Protocol: Pharmacokinetics of Advantage Arrest

Protocol version: 2016-11-08 NCT04184271 Document Date: 11/08/2016

Sponsor:	Advantage Silver Dental Arrest, LLC [name] United States
Investigator:	[name] University of Washington [name] United States Email: [contact] [contact]
Sub-investigators:	[name] University of Washington [contact]
	[name], PhD University of California, San Francisco [contact]
Research Site:	University of Washington Regional Clinical Dental Research Center [name] United States [contact]
Regulatory Monitor:	[name] Cooley Consulting, Inc. [name] United States [contact]

Purpose of the Study and Background

Objective: The purpose of this study is to characterize basic PK parameters (Cmax, $t_{1/2}$, AUC, and total urinary recovery) to contribute to evidence for the safety of Advantage Arrest, consistent with Guidance for Industry--Exposure--Response Relationships (April 2003). On a preliminary basis, we will also characterize the microbiome before and 24-hours after the topical treatment.

Background: The Sponsor/Investigator conducted a preliminary PK study in six adults (Vasquez et al., 2012) in which 38% diammine silver fluoride (silver diamine fluoride) was applied topically to three teeth in each subject and maximum serum concentration and time to maximum serum concentration were studied over four hours. Mean amount of the agent applied was 7.57 mg. Over the four-hour observation period the mean maximum serum concentrations were 1.86 umol/L for fluoride and 206 nmol/L for silver. These maximums were reached at 3 h and 2.5 h for fluoride and silver, respectively. Fluoride exposure was below the EPA oral reference dose. Silver exposure exceeded the EPA oral reference dose for cumulative daily exposure over a lifetime, but for occasional use was well below concentrations associated with toxicity. Nevertheless, the number of subjects was limited and the follow-up period too short to calculate the AUC. Although diammine silver fluoride is available in many countries, there are no other published PK studies to our knowledge.

Assumptions: This is a topical agent where the active ingredients are applied to the teeth and eventually swallowed and may be absorbed through the GI tract or excreted. Minimal amounts are absorbed through the oral mucosa. Serum concentrations of silver and fluoride will be be proportional to the dose of silver and fluoride administered topically to the teeth as part of Advantage Arrest. The total urinary recovery of fluoride, adjusted for baseline levels, will be calculated to estimate the minimum amount absorbed in each patient following application of the varnish. As biliary excretion is the principle route of elimination of silver (Lansdown et al., 2010), it is unlikely that significant amounts of silver will be recovered in the urine.

Criteria for Subject Selection

Number of subjects: There will be up to 20 healthy adult subjects enrolled in the study with the goal of at least 16 subjects to complete the study.

Gender of subjects: The subjects will be approximately half male and half female. **Age of subjects:** Subjects must be 18 years of age or older.

Racial and Ethnic Origin: In a small study it is not possible to fully represent the racial/ethnic distribution of the region or US. The investigator will attempt to recruit a racial/ethnic diverse population.

Inclusion criteria: Subjects will have at least 20 teeth. Subjects will be healthy and taking no prescription or OTC medications, including topical fluoride gels or rinses. Healthy status will be determined by self-reported medical history by the attending clinician.

Exclusion criteria: Subjects will be excluded if they have oral mucositis or any ulcerative lesions or hypersensitivity to silver or fluoride. Subjects who are pregnant, breastfeeding, or weigh less than 110 pounds will not be eligible to participate.

Methods and Procedures

Design of the Study and Minimization of Bias: Open label exposure--response study.

Randomization: Not applicable

Blinding: Not applicable

Baseline procedures: When informed consent has been obtained, age, race, gender, and ethnicity information will be collected at baseline along with a brief health history. A brief visual examination will be conducted to note any evidence of inflammatory or ulcerative changes to the gums or other oral tissues. Non-fluoride toothpaste will be used on the day of the baseline appointment through the 24-hour blood draw period. An 18 gauge sterile venous cannula will be placed in an upper extremity. An initial blood sample of 6 mL (one tube for serum collection) will be withdrawn using a fluoride free tube (BD Vacutainer with Clot Activator Plus Royal Blue Stopper). Subject will void for a baseline urine sample collection. Using a dental microbrush, dental plaque will be collected from the buccal surfaces of the upper posterior teeth and the microbrush inserted in a sampling tube and agitated.

Study intervention: Advantage Arrest, Aqueous Diamine Silver Fluoride [Ag(NH₃)]₂F, CAS RN 33040-28-7, 38.3% to 43.2% in purified water 5.0 - 5.9% (w/v) fluoride; 24.4 - 28.8% (w/v) silver, Silver Diamine Fluoride

Teeth will be brushed with a soft toothbrush to remove debris and dried with cotton prior to application. The specific procedure is that 5 mg (1 drop) of Advantage Arrest will be dispensed into a plastic dappen dish and all of the material will be applied to the facial cervical surfaces of 5 posterior teeth with an applicator. To calculate the amount of Advantage Arrest applied: the dappen dish with the initial amount of Advantage Arrest dispensed and applicator will be weighed before application and after application. The amount applied will be calculated as the difference in weights before and after application. The amount applied will be recorded. The teeth will remain isolated with cotton rolls for 3 minutes and then rinsed with water and high volume evacuation. Subjects will not eat for at least 2 h following application of the test agent.

Blood, urine and plaque sampling following intervention:

Subjects will have blood samples of 6 mL withdrawn at 30 min, 1h, 2h, 3h, 4h, 6h, 8h, 12h and 24 hours. Urine will be collected for a 24-hour cumulative sample following application of the study intervention. Subjects will continue to collect urine in the original container until 12h and be provided instructions and a container to continue the urine collection to 24 hours. Subjects will remain at the research site through the 12 hour blood and urine collection and return for the 24-hour timepoint. A 24-hour plaque sample will be obtained in the same manner as the baseline sample.

Blood, urine and plaque sample processing:

Blood samples will be spun in a clinical centrifuge, the serum withdrawn, and then the serum will be frozen for later analysis. The total volume of urine at baseline, 12 and 24 hours will be recorded and a 10 mL aliquot will be taken of each sample and frozen for later analysis. Plaque samples will be placed in a receiving tube, the tube agitated, and the contents frozen for later analysis.

Sample Analysis: Serum and urine samples will be analyzed for F- by ion chromatography and Ag+ by ICPMS (Inductively coupled plasma mass spectrometry). Cmax, Tmax, Cmin (last measurable time point), $t_{1/2}$, and the AUC will be calculated from serum samples. Total amount recovered will be calculated from urine samples. Plaque will be analyzed by 16S ribosomal RNA profiling.

Data Analysis and Monitoring:

Subject disposition: The frequency and reason for subject withdrawal will be summarized.

Data Analysis and reporting: The PI and sub-investigators will be responsible for performing all analyses, creating the output for the analyses and disseminating results to the study team. The Principal Investigator and the rest of the study team will then review the results. The Principal Investigator will be responsible for drafting and preparing a final report of the study.

Data Storage and Confidentiality

The data will be stored on password protected computers in the Clinical Research Center at the UWMC and in a locked cabinet and on password protected computers at the Regional Clinical Dental Research Center at the University of Washington School of Dentistry. Only investigative personnel will have access. The data will be available for inspection by regulatory monitors and FDA.

Risk-Benefit Assessment

Risk Category: Greater than Minimal Risk

Potential Risk: Hypersensitivity to silver or fluoride, changes to intraoral tissues: erythema, gingival inflammation, or soft tissue changes. Advantage Arrest has been used extensively since clearance as a medical device in 2014 and the Sponsor knows of no adverse effects. The same agent is approved in Japan and there have no harms reported. There may be bruising at the site of the blood collection.

Protection Against Risks: The study will be carried out in the Clinical Research Center at the University of Washington Medical Center and the Regional Clinical Dental Research Center at University of Washington School of Dentistry by licensed personnel under the Institute of Translational Health Sciences.

Potential Benefits: There is no direct benefit to the participant.

Alternatives to Participation: The alternative is to decline participation.

Subject Identification, Recruitment and Consent/Assent

Method of Subject Identification and Recruitment:

Subjects will be recruited from among University of Washington (UW) employees, patients, or visitors. Flyers will be posted in the UW Health Sciences to notify potential subjects of the opportunity to participate. They will call or email staff at the School of Dentistry Regional Clinical Dental Research Center (RCDRC) for more information or to schedule an appointment. Subjects who meet the study's criteria for entry will be recruited into the study by the dental staff and enrolled.

Process of Consent: Potential participants will have the opportunity to ask questions and will be informed that participation is voluntary. They will have the opportunity to take the consent home to consider whether or not they want to take part in the study. They will be reminded that whether or not they decide to participate will not affect their care at the UWMC or the School of Dentistry and they can ask questions about participation or discontinue participation at any time.

Subject Capacity: Participants must have the capacity to give informed consent, be English speaking and able to read and understand English.

Subject / Representative Comprehension: Potential participants will be asked to clarify their understanding of the objectives of the study. They will also be asked to clarify their understanding of the risks and benefits of participation.

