Analysis Plan: Pharmacokinetics of Advantage Arrest

NCT04184271

Document Date: 07/30/2020

For the pharmacokinetic analysis, baseline serum fluoride and silver concentrations will be assessed and when appropriate, subtracted from other timed serum concentrations to adjust for baseline levels.

Pharmacokinetic analysis will be performed using Phoenix WinNonlin (Certara).

- The time to peak concentration (T_{max}), observed and baseline-corrected peak concentrations (C_{max}), and observed 24-h concentration (C_{24 h}) will be reported.
- The elimination rate constant (k_{elim}) will be determined by nonlinear regression with a minimum of 3 time points with decreasing concentrations over time observed after the peak concentration.
- Half-life (t_{1/2}) will be calculated as ln(2)/k_{elim}.
- Area under the curve (AUC): The 24-hour AUC (AUC_{0-24 hr}) will be calculated using a log-linear trapezoidal rule of baseline-corrected serum concentrations from time = 0 to 24 h. The AUC_{0-∞} will be calculated using a log-linear trapezoidal rule of baseline-corrected serum concentrations and extrapolated to infinite time by C_{24hour}/k_{elim}, where C_{24hour} is the 24 hour concentration.
- The percent extrapolated AUC will be calculated as $(AUC_{0-\infty} AUC_{0-24 \text{ hr}})/AUC_{0-\infty} \times 100$.
- The total urinary recovery of fluoride and silver will be determined by multiplying the concentration measured in the urine collected over 24 hours by the total volume of urine collected over 24 hours.

Statistical analysis will be performed using Excel to calculate the mean \pm standard deviation for the pharmacokinetic parameters. No statistical comparisons will be made as it is a single arm study.

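### The SAP's urinary fluoride recovery has no baseline term although the protocol promises one; separately, dietary fluoride is neither standardised nor recorded

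*Protocol*

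**What the plan says.** **Urine.** The protocol (Assumptions) states: "The total urinary recovery of fluoride, adjusted for baseline levels, will be calculated to estimate the minimum amount absorbed in each patient". A baseline void is collected (Baseline procedures). Urine volume is recorded and an aliquot frozen at baseline, 12 h and 24 h (sample processing). The last bullet of the SAP obtains recovery by "multiplying the concentration measured in the urine collected over 24 hours by the total volume of urine collected over 24 hours". It has no baseline term and does not refer back to the protocol's adjustment.

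**Serum.** The protocol takes one sample before application: "An initial blood sample of 6 mL (one tube for serum collection) will be withdrawn". The SAP assesses the baseline concentration and has it "when appropriate, subtracted from other timed serum concentrations to adjust for baseline levels". AUC uses a "log-linear trapezoidal rule of baseline-corrected serum concentrations from time = 0 to 24 h", and for Cmax the SAP reports "observed and baseline-corrected peak concentrations".

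**Control of other fluoride.** Baseline procedures: "Non-fluoride toothpaste will be used on the day of the baseline appointment through the 24-hour blood draw period". The inclusion criteria rule out topical fluoride gels and rinses, and Study intervention bars eating for at least 2 h after application. Subjects stay on site to 12 h and return at 24 h; the only take-away instructions mentioned concern urine collection. Neither document states a rule or a record for water, other drinks, food before application or food after 2 h.

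**Design.** The SAP closes with "No statistical comparisons will be made as it is a single arm study".

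**The concern.** Total urinary recovery is one of the PK parameters named in the protocol's objective. It is a lower bound on absorption only if the fluoride counted came from the product. People excrete fluoride from water and diet whether or not they are treated. The SAP formula attributes all of it to the product, even in a subject whose intake never changes. The two documents therefore define different quantities under one name, and the SAP's version does not support the protocol's interpretation.

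The serum problem is narrower. Subtracting one value taken before application removes a steady background exactly. It does not remove a later change, such as one shared by subjects who all start to eat and drink once the 2 h restriction ends, close to the 3 h fluoride peak reported in Background. With one arm, no untreated day and no intake record, such a change cannot be separated from product afterwards.

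**Working it through.** The documents give no figure for either effect, so there is none to reproduce. The calculations below show scale; every assumed input is marked.

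**1. What the urine formula measures.** Let A be fluoride absorbed from the product, f (at most 1) the fraction of A excreted in urine within 24 h, and B the background fluoride excreted in the same 24 h.

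- Protocol intention: recovery minus background = fA, which cannot exceed A. This is a lower bound.
- SAP formula: recovery = fA + B. This stays at or below A only if B is no larger than (1 − f)A.

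**2. Fluoride in the product.** Inputs from Study intervention: 5 mg applied, 5.0 to 5.9% w/v fluoride (50 to 59 mg/mL). Density is assumed.

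| Amount | Density 1.0 g/mL (assumed) | Density 1.3 g/mL (assumed) |
|---|---|---|
| 5 mg | 0.250 to 0.295 mg | 0.192 to 0.227 mg |
| 7.57 mg (mean in the earlier study, Background) | 0.379 to 0.447 mg | 0.291 to 0.344 mg |

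**3. Scale of the missing term.** One litre of water at an assumed 0.1 to 1.0 mg/L carries 0.1 to 1.0 mg.

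- Against 5 mg of product: 0.1/0.295 = 0.34 to 1.0/0.192 = 5.2 times.
- Against 7.57 mg: 0.1/0.447 = 0.22 to 1.0/0.291 = 3.4 times.

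These ratios compare intakes. They carry over to recovery only if fluoride from water and from product is absorbed and excreted alike (assumed).

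**4. What a baseline adjustment would leave.** Steady intake would largely cancel; only a change would remain. At an assumed 1.5 L drunk and density 1.0, a change of 0.25/1.5 = 0.17 to 0.295/1.5 = 0.20 mg/L in the fluoride content of drinks equals the fluoride in the whole 5 mg dose.

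**5. Serum illustration.** The Background peak is scaled by dose, following the protocol's own proportionality assumption: C = 1.86 × 5/7.57 = 1.23 umol/L at 3 h. Assume a linear rise to 3 h, then exponential decay with k = ln 2/t½ and t½ of 3, 6 or 12 h.

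AUC0-24 = 3C/2 + (C/k)(1 − exp(−21k)) = 7.12, 11.54 and 16.79 umol·h/L.

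Add a shared shift to the 3, 4, 6, 8 and 12 h samples only and recompute by trapezoids at the protocol's sampling times (linear while rising, logarithmic while falling, which is one reading of the SAP's rule):

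| Shift (assumed) | t½ 3 h | t½ 6 h | t½ 12 h |
|---|---|---|---|
| +0.1 umol/L | +1.25, 17.5% | +1.34, 11.7% | +1.43, 8.5% |
| +0.05 umol/L | +0.63, 8.8% | +0.68, 5.9% | +0.72, 4.3% |

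A fall of the same size lowers AUC by nearly the same percentages.

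**6. Sensitivity.** With the unscaled 1.86 umol/L peak, AUC0-24 is 10.78, 17.47 and 25.42, and the +0.1 shift adds 1.25/10.78 = 11.6% at t½ 3 h and 1.43/25.42 = 5.6% at 12 h. Background does not say whether 1.86 was net of baseline; if half of it was background, the percentages in the table about double.

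**The case against.** **Most of the case against concerns size and remedy, and much of it stands.**

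- *The urine multiples could be read as the effect of uncontrolled diet.* They are not. They size the missing baseline term. With the protocol's adjustment in place, only a change in intake would remain (step 4).
- *A reader might infer a larger serum error.* A 0.1 umol/L offset held for all 24 h adds 2.4 umol·h/L, or 14 to 34% of the scaled AUC. That needs a step just after the baseline sample that lasts a full day in every subject. Food cannot cause it, because eating is barred for 2 h, and nothing in the documents points to it.
- *Independent offsets between subjects are not a bias.* With SD 0.1 and 16 completers, 0.1 × 24/√16 = 0.6 umol·h/L, or 4 to 8% of AUC, is one standard error of the mean. The expected bias is zero.
- *The inputs are assumed.* Water fluoride, volume, density, half-life and serum shift come from neither document.
- *Instructions may exist elsewhere.* Consent pages are not in the public documents and unit practice during the 12 h stay is not visible. One cannot conclude that subjects had no dietary instructions, only that these documents state none.
- *The obvious urine correction is crude.* Baseline-void concentration × 24 h volume treats one spot value as the day's average. If that void is twice as concentrated as the average background, 2B is subtracted, leaving fA − B, which can be negative.
- *The stakes are limited.* Upward contamination overstates exposure, which is conservative for safety; Background puts earlier fluoride exposure below the EPA oral reference dose; the study is descriptive.

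None of this supplies the baseline term that the protocol promises. A falling background would also understate serum exposure, so the serum error is not always conservative.

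**Conclusion.** **Urine: wrong as written.** The SAP formula omits the adjustment the protocol promises, and its result cannot be read as a lower bound on absorbed fluoride. This follows from the two texts alone. Its size does not: the 0.3 to 5.2 ratio rests on assumed water fluoride, 1 L drunk and density 1.0 to 1.3 g/mL, and the upper end combines the most unfavourable values.

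**Diet and serum: a cheap improvement, not an error in the formula.** Steady habitual intake does not bias corrected serum. A change shared by subjects after the baseline sample does, in either direction, by about 4 to 18% of AUC0-24 under the assumed 0.05 to 0.1 umol/L shift and 3 to 12 h half-life. The true size cannot be set from the documents.

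A reader might infer that the fluoride safety conclusion fails or that the silver results are affected. The documents support neither. What suffers is the accuracy of the fluoride PK, which the study exists to describe.

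**What to change.** **SAP, at any stage:**

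- Put a baseline adjustment into the urinary fluoride formula, for example by subtracting baseline-void concentration × 24 h volume, and report recovery with and without it.
- State that a correction from one spot void is approximate because it depends on hydration.
- Do not describe unadjusted recovery as the least amount absorbed.
- State that fluoride AUC, Cmax, half-life and recovery may include dietary fluoride.

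This costs a few sentences and one extra column of results. The baseline volume and aliquot are already in the protocol.

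**Protocol, only if samples are not yet collected:**

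- Record the time of the void before the baseline void, so that a background excretion rate can be formed.
- Provide the same low-fluoride water and standard meals to all subjects on site.
- Give a written instruction to use the same water from before baseline through 24 h.
- Keep a one-page record of food and drink over that period.

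The costs are water, meals, a form and a slight burden on subjects. If the change of water starts too close to baseline, background may still be falling during sampling, so the regimen should begin well before the baseline sample and run unchanged to 24 h.

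### Fluoride toothpaste is allowed until the evening before dosing, so subtracting the single pre-dose value as a constant can understate baseline-corrected serum fluoride AUC0–24

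*Protocol*

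**What the plan says.** Protocol, Baseline procedures: "Non-fluoride toothpaste will be used on the day of the baseline appointment through the 24-hour blood draw period". Neither document asks for an earlier stop. The inclusion criteria require subjects to be "taking no prescription or OTC medications, including topical fluoride gels or rinses"; ordinary toothpaste is not named.

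There is one pre-dose serum sample ("An initial blood sample of 6 mL (one tube for serum collection) will be withdrawn using a fluoride free tube") and one pre-dose urine collection ("Subject will void for a baseline urine sample collection").

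The SAP says that baseline serum fluoride and silver will be assessed and, "when appropriate, subtracted from other timed serum concentrations to adjust for baseline levels". It gives no criterion for when subtraction is appropriate. AUC0–24 is "calculated using a log-linear trapezoidal rule of baseline-corrected serum concentrations from time = 0 to 24 h", and AUC0–∞ also starts from corrected values. Cmax is reported both observed and corrected; C24h is reported as observed.

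For urine the documents differ. Protocol, Assumptions: "The total urinary recovery of fluoride, adjusted for baseline levels, will be calculated". The SAP's recovery is 24-hour urine concentration times 24-hour volume, with no baseline term.

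**The concern.** The protocol treats toothpaste as a fluoride source worth removing, but its rule mainly protects the samples taken after dosing. The sample used to correct all the others may still follow fluoride brushing the evening before. Any residual from that brushing goes on falling after dosing, while the subtracted amount stays fixed, so the later samples are over-corrected.

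The study is meant to contribute safety evidence, and AUC and Cmax are among its named parameters. Understating systemic fluoride is the non-conservative direction. With one arm and 16 to 20 subjects, nothing in the design would reveal a shared shift. The time of last fluoride toothpaste use is not recorded, so the shift could not be assessed afterwards either.

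**Working it through.** The documents give no figure for baseline fluoride, toothpaste carry-over or fluoride half-life, so there is no stated figure to reproduce. What follows is a sensitivity calculation.

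**Inputs from the documents**
- Product dispensed: 5 mg. Fluoride content: 5.0–5.9% w/v (Study intervention).
- Interval: 0 to 24 h, one pre-dose value (Baseline procedures; SAP).

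**Assumed inputs**
- Product density 1.0–1.3 g/mL. Fluoride dose D is then from 5/1.3 × 0.050 = 0.192 mg (10.1 µmol) to 5/1.0 × 0.059 = 0.295 mg (15.5 µmol).
- One compartment, full absorption, half-life 3–9 h, volume V = 40 L where concentrations are needed.
- S = 0.05–0.15 mg fluoride swallowed at one brushing, t = 10 h before dosing. Other background is flat.

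**Formulas**, with k = ln 2 / half-life
- Residual at dosing: r = (S/V) × exp(−kt).
- AUC0–24 error from subtracting r as a constant: r × [24 − (1 − exp(−24k))/k].
- Product AUC0–24: D/(kV) × (1 − exp(−24k)).
- Relative loss, in which V cancels: (S × exp(−kt)/D) × [24k/(1 − exp(−24k)) − 1].

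**Results for S = 0.1 mg, t = 10 h**

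| Half-life | exp(−10k) | Bracket | Loss, D = 0.295 mg | Loss, D = 0.192 mg |
|---|---|---|---|---|
| 3 h | 0.099 | 4.57 | 15% | 24% |
| 5 h | 0.250 | 2.45 | 21% | 32% |
| 9 h | 0.463 | 1.19 | 19% | 29% |

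Central case in concentration units (half-life 5 h, V = 40 L): S = 0.1 mg = 5.26 µmol, so r = 5.26/40 × 0.25 = 0.033 µmol/L. The error is 0.033 × 17.05 = 0.56 µmol·h/L, against a product AUC0–24 of 1.76–2.69, or 21–32%. Over S = 0.05–0.15 mg the full range is about 8–48%.

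**Second parameterisation.** Assume r = 0.1 µmol/L and a product increment of 1.0 µmol/L peaking at 3 h, with the protocol's sampling times. The AUC0–24 loss is about 17%, 19% and 10% at half-lives of 3, 6 and 10 h.

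**Corrected Cmax.** With the peak at 3 h, the loss is r × (1 − exp(−3k)). For S = 0.1 mg this is 0.007–0.013 µmol/L, about 2–5% of D/V (0.25–0.39 µmol/L). The second parameterisation gives 2–5%.

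**Larger dose.** With D = 5 × 0.25 = 1.25 mg and S = 0.1 mg, the AUC0–24 loss at 10 h falls to about 4–5%.

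**Negative values.** The formula lets late corrected values go below zero. The SAP does not say how these are handled. Setting them to zero reduces the loss: in the second parameterisation at a 3 h half-life, from 17% to 11%.

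**Effect of an earlier stop.** In the worst case over the assumed inputs (S = 0.15 mg, D = 0.192 mg, half-life 9 h):
- One day earlier (t = 34 h): 0.781 × 0.0729 × 1.19 = 6.8%.
- Two days earlier (t = 58 h): 0.781 × 0.0115 × 1.19 = 1.1%.

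**The case against.** **The net direction is not fixed.** A reader might infer that every subject's exposure is shifted downward. That needs the rest of the background to stay flat for 24 h. The protocol restricts only eating, for 2 h, and neither document controls fluoride in food or drink. In the central case a mean background rise of 0.56/24 = 0.023 µmol/L cancels the loss, and a larger rise reverses it. This stands. Diet is a second uncontrolled error, though, and does not remedy the first.

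**Urine does not follow serum.** A reader might infer that recovery is also biased low. The SAP formula subtracts nothing, so residual toothpaste fluoride excreted after dosing would raise recovery. A downward bias could arise only under the protocol's baseline adjustment, for which no method is given.

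**Subtraction is conditional, and uncorrected values are reported.** The SAP subtracts only when appropriate, and observed Cmax and C24h are untouched. This stands, but the AUC definitions use corrected values, and no observed AUC is planned.

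**Same-day brushing.** Fluoride brushing 2 h before dosing would give losses from 17% to over 100% in the same model, but it would breach the stated rule. The documents do not say when subjects are told of the rule, and consent may be taken home beforehand. That is a gap in communication and does not support using the 2 h range as the expected size.

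**The size rests on assumptions.** Swallowed amount, half-life, absorption and brushing time are not in the documents. The percentages are large because the 5 mg dose holds little fluoride. The pilot's mean maximum of 1.86 µmol/L, not stated to be baseline-corrected, leaves the model's product increment unverified. This stands, and it is why the result is given as a range.

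**Conclusion.** The point holds for baseline-corrected serum fluoride AUC0–24, where subtraction is applied and the pre-dose value contains a declining toothpaste residual. Following the toothpaste rule exactly permits this. Under the stated assumptions the loss is about 8–48% for brushing 10 h before dosing (about 15–32% at 0.1 mg swallowed), and it shrinks in proportion if the true fluoride dose is larger. The effect on corrected Cmax is a few per cent.

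The documents do not support a general claim that fluoride exposure is understated. AUC0–∞ could move either way, because the SAP does not say whether the 24-hour concentration in the extrapolated tail is corrected, and over-subtraction steepens the terminal slope. The carry-over concerns fluoride only, not silver.

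**What to change.** - Start the non-fluoride toothpaste before the baseline day: at least one full day, for example two. Under the worst assumed inputs, one extra day leaves at most about 7% AUC0–24 bias and two days about 1%.
- Tell subjects the rule and supply the toothpaste when the appointment is scheduled or at consent.
- Record the date and time of last fluoride toothpaste use, so that any remaining carry-over can be judged.
- Reconcile the protocol's baseline adjustment of urinary fluoride recovery with the SAP formula.

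The cost is a tube of toothpaste and one line on the case report form. Subjects go a day or two without fluoride toothpaste, and consent and dosing cannot fall on the same day unless the rule was already followed. The change does not address fluoride from food or drink.

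### The single untimed baseline void cannot give the background excretion rate that baseline-adjusted urinary fluoride recovery needs, and the SAP formula has no urine baseline term

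*Protocol*

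**What the plan says.** Total urinary recovery is one of the PK quantities named in the protocol's Objective. The Assumptions paragraph states how it is to be used for fluoride: "The total urinary recovery of fluoride, adjusted for baseline levels, will be calculated to estimate the minimum amount absorbed in each patient".

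The urine available is as follows.

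- **Before dosing** (Baseline procedures): "Subject will void for a baseline urine sample collection". No start time, time of the previous void or collection interval is asked for.
- **After dosing** (sampling section): "Urine will be collected for a 24-hour cumulative sample following application of the study intervention", with one container to 12 h and another from 12 h to 24 h.
- **Recorded** (sample processing section): "The total volume of urine at baseline, 12 and 24 hours will be recorded", and an aliquot of each sample is frozen. The Sample Analysis paragraph names fluoride and silver assays only, so no marker of urine dilution is planned.

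The SAP defines urinary recovery as "multiplying the concentration measured in the urine collected over 24 hours by the total volume of urine collected over 24 hours". Its baseline correction is described for serum only: baseline values are, where appropriate, "subtracted from other timed serum concentrations to adjust for baseline levels".

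**The concern.** Background fluoride excreted over the 24 hours after dosing is a rate multiplied by 24 h. A single void of known volume and concentration gives an amount accumulated over an unknown time. Recording the baseline volume does not help without the interval.

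This is separate from the SAP's omission of a baseline term. Writing a term into the formula would still leave the void without the quantity that the term needs.

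What is at stake is the per-subject claim. If the adjustment subtracts too much, net recovery is too low and may be negative. If it subtracts too little, the result is no longer a lower bound on what that subject absorbed. The signal is small because the product is applied in milligram amounts, so a modest error in the background can be large beside it.

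**Working it through.** The plan states no figure to reproduce: it gives no background urinary fluoride level and no rule for scaling the void to 24 h.

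**Inputs from the documents.** Stated amount: "5 mg (1 drop) of Advantage Arrest will be dispensed into a plastic dappen dish". Fluoride content: "5.0 - 5.9% (w/v) fluoride". Mean amount applied in the preliminary study (Background): 7.57 mg.

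**Assumptions, not in the documents.** Product density 1.0–1.3 g/mL; background excretion B = 0.3–1.0 mg per 24 h, constant before and after dosing; flow ratio r (post-dose over baseline).

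**1. Fluoride in the stated amount** = mass / density × content.
- Density 1.0: 5 mg is 0.005 mL; × 50–59 mg/mL = 0.250–0.295 mg.
- Density 1.3: 0.00385 mL × 50–59 mg/mL = 0.192–0.227 mg.
- Overall range: 0.19–0.30 mg.

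**2. Trying to form a rate.** Background over 24 h = (C₀ × V₀ / h) × 24, where C₀ and V₀ are the void's concentration and volume and h is the hours since the previous void. C₀ and V₀ are available; h is not. To illustrate with an assumed 0.25 L void at 0.5 mg/L (0.125 mg): h = 2 gives 1.5 mg per 24 h and h = 4 gives 0.75 mg. Mistaking one for the other moves the background by 0.75 mg.

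**3. Scaling by concentration instead.** Let f₀ be urine flow during the baseline interval. Then C₀ = (B/24)/f₀ and the 24-hour volume is 24 × r × f₀. The estimated background is C₀ × V₂₄ = r × B, so the error is (r − 1) × B.

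| r | Error for B = 0.3–1.0 mg | Effect |
|---|---|---|
| 2 | +0.3 to +1.0 mg | subtracts too much |
| 1.25 | +0.075 to +0.25 mg | subtracts too much |
| 0.5 | −0.15 to −0.5 mg | subtracts too little |

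**4. When the error reaches the dose fluoride.** This requires B ≥ dose fluoride / |r − 1|.
- r = 2: B of at least 0.19–0.30 mg, which is met across the assumed range.
- r = 0.5: B of at least 0.38–0.59 mg, which is met only in the upper part.
- r = 1.25: B of at least 0.77–1.18 mg, which is mostly not met.
- At 7.57 mg and density 1.0, dose fluoride is 0.38–0.45 mg, so r = 2 with B = 0.3 mg no longer reaches it.

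**5. SAP formula as written.** With no baseline term, all of B is counted as recovery, an excess of 0.3–1.0 mg on the same assumption.

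**The case against.** The strongest reply is that the void is not the only source of a background estimate. Two routes use data already planned.

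- **The 12–24 h urine** has a known interval, a volume and an aliquot, so it gives a rate. Any dose fluoride still being excreted would make it subtract too much, which keeps the result a lower bound if background is steady. Overnight variation is a caveat.
- **Renal clearance** = 24-hour urinary amount / observed serum AUC over 24 h. Background = clearance × baseline serum concentration × 24 h. This needs constant clearance and a constant background; the SAP's serum subtraction already relies on the second.

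This stands. A reader might infer that the design leaves no way to adjust for background; the documents do not support that. They show only that the void cannot supply the rate, and that neither alternative is written into the plan.

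It also stands that no document scales the void by concentration. That is one way to carry out the protocol's promise, not a planned step.

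The size is open to challenge too. B and r are assumed, and 5 mg is nominal because the amount applied is weighed for each subject. If a drop were 25 µL (assumed), it would hold 1.25–1.48 mg fluoride, above the r = 2 error throughout. It is tempting to suppose that subjects arrive with a concentrated morning void and then drink freely at the site. No section gives an appointment hour or a fluid rule, so the direction of the error is unknown.

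Finally, the SAP reports means, and random error partly averages out: with an assumed background of 0.8 mg/day and 50% CV, the SD is 0.40 mg and the standard error for 16 subjects is 0.40/√16 = 0.10 mg. That does not answer a promise made for each patient, and a systematic difference would not average out.

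**Conclusion.** The point holds in a limited form. On the documents alone, the protocol promises a per-subject baseline adjustment, the baseline void as specified cannot yield the rate needed for it, and the SAP formula omits the adjustment. The protocol and SAP must be reconciled on this.

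The size is conditional. On the assumed B, a void scaled by concentration is wrong by 0.3–1.0 mg at r = 2 and by 0.15–0.5 mg at r = 0.5, against 0.19–0.30 mg of fluoride in the stated amount. A reader might infer that any adjusted figure must be wrong by more than the whole dose. The documents do not support that: the error is smaller than the dose fluoride when background is low, flow changes little, or more product is applied.

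One named objective is affected. The serum parameters are not, and the adjustment is promised for fluoride only.

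**What to change.** - Record the clock time of the last void before the baseline void, and of the baseline void itself, with the bladder fully emptied just before application.
- Compute background as concentration × volume / hours, and subtract that rate × 24 h from 24-hour recovery. Add this term to the SAP.
- As a sensitivity check, estimate background from the 12–24 h urine and from renal clearance × baseline serum concentration × 24 h.

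**Cost.** Two clock times per subject (the earlier one from recall), with no extra sample, assay or visit. A short baseline interval still misses time-of-day and day-to-day variation. A full timed home collection would cost more: baseline procedures follow consent, so the container would have to be handed over beforehand.

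**If collection is already complete**, use the two planned-data estimates, report unadjusted recovery alongside, and do not present a void-based adjusted figure as a lower bound on each subject's absorption.
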